6.7 BASELINE, TIME WINDOWS AND CALCULATED VISITS

Randomisation is defined as Day 1 and it is planned that the alteplase patients are administered their initial 2h infusion of study medication within 6 hours of randomisation, on Day 1 (Visit 2a). The last planned administration of study medication for the alteplase patients is the long term 12h infusion on Day 5.

Since all patients are on SOC and there is no clear start or stop of SOC, a fixed treatment duration will be used for all patients, for the purposes of the analyses. Therefore, endpoints referred to as ‘on treatment’ will include all relevant events from the relevant start point plus 288 hours (last planned treatment on Day 5 + 7 days of REP = 12 days = 288 hrs).

However, to take account of the fact that some patients may have had treatment interruptions, the residual effect period should be in relation to the last intake of alteplase infusion. [Table 6.7: 1](#) below outlines the time period definitions for counting on treatment safety event.

Table 6.7: 1 Time period for counting on treatment safety events

On treatment	Start point	End date
SOC patients	Randomisation date/time	Start point + 288 hrs
Alteplase patients	First administration of alteplase date/time	Latest of: 
 Start point + 288 hrs Last administration of alteplase date/time + 168 hrs

[Note: 288 hrs represents 12 days, 168 hrs represents 7 days]

According to CTP Version 3 Section 1.2, the residual effect period (REP) is 7 days.

As outlined in CTP Version 3 Section 7.2.1, the term "baseline" refers to the last observed measurement prior to randomisation on Day 1.

7. PLANNED ANALYSIS

The tables that are created from the statistical analysis will follow the format of the standard within BI [\(8\)](#).

The overall disposition of the patients in the trial will be presented, together with the number of patients discontinuing prior to day 28, and vital status at day 90.

The number of patients participating in the study by country and the number of sites, for each of the patient populations will be summarised.

Demography and baseline characteristics will be presented, as well as the stratification used at the time of the patient randomisation. A summary of the iPDs will be provided.

Where statistical comparisons are indicated, they will be done by comparing alteplase versus SOC.

All descriptive analyses will be performed:

- within the NIV patient cohort as the main cohort
- within the IMV patient cohort as the exploratory cohort
- on the NIV and IMV cohorts pooled – additional select efficacy analyses for primary and secondary efficacy endpoints

For the NIV patient cohort, the default set of covariates for adjustment in analyses are:

- Baseline D-Dimer status (≥ 3 to < 5 , ≥ 5 -fold ULN)
- Age
- Number of days of NIV support
- Baseline value of the $\text{PaO}_2/\text{FiO}_2$ ratio – only for the endpoint $\text{PaO}_2/\text{FiO}_2$ ratio change from baseline to Day 6

For the IMV patient cohort, the default set of covariates for adjustment in analyses are:

- Baseline D-Dimer status (≥ 3 to < 5 , ≥ 5 -fold ULN)
- Age
- Baseline WHO value (7, 8, 9)
- Baseline value of the $\text{PaO}_2/\text{FiO}_2$ ratio – only for the endpoint $\text{PaO}_2/\text{FiO}_2$ ratio change from baseline to Day 6

For efficacy analyses, patients will be analysed according to the patient information given in the CRF, in the case of potentially erroneous data entered into the interactive response technology (IRT). This is related to the baseline information, ventilation support (NIV, IMV) and D-Dimer level (≥ 3 to < 5 , ≥ 5 -fold ULN).

In general, for End-Of-Text tables, the set of summary statistics is: N (number of patients with non-missing values) / Mean / SD / standard error (SE) / Min / Q1 (lower quartile) / Median / Q3 (upper quartile) / Max.

Statistical parameters will be displayed to a defined number of decimal places as specified in the BI guideline "Reporting of Clinical Trials and Project Summaries" [\(9\)](#).

Tabulations of frequencies for categorical data will include all possible categories and will display the number of observations in a category as well as the percentage (%) relative to the respective treatment group (unless otherwise specified, all patients in the respective patient set whether they have non-missing values or not). Percentages will be rounded to one decimal place. The category missing will be displayed only if there are actually missing values.

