3.3.2 Inclusion criteria

Patients participating in Part 1 are not eligible for Part 2.

1. Age \geq 18 years-(or above legal age)
2. ARDS with $\text{PaO}_2^*/\text{FiO}_2$ ratio >100 and ≤ 300 , either on non-invasive ventilator support, OR on mechanical ventilation (<48 hours since intubation),
 - with bilateral opacities in chest X-ray or CT scan (not fully explained by effusions, lobar/lung collapse, or nodules)
 - with respiratory failure (not fully explained by cardiac failure/fluid overload)

*or estimation of $\text{PaO}_2/\text{FiO}_2$ from pulse oximetry ($\text{SpO}_2/\text{FiO}_2$) (see [Appendix 10.2](#) for $\text{SpO}_2/\text{FiO}_2$ estimation)
3. SARS-CoV-2 positive (laboratory-confirmed RT PCR test)
4. Fibrinogen level \geq lower limit of normal (according to local laboratory)
5. D-Dimer \geq upper limit of normal (ULN) according to local laboratory
6. Signed and dated written informed consent in accordance with ICH Good Clinical Practice (GCP) and local legislation prior to admission to the trial.

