7. STATISTICAL METHODS AND DETERMINATION OF SAMPLE SIZE

The eligible patients for this trial will be randomised in Part 1 to one of three treatment arms

- alteplase 0.3mg/kg over 2 hours, followed by daily long-term (12h) infusion of 0.02 mg/kg/h over 5 days, “alteplase dosing regimen A”
- alteplase 0.6mg/kg over 2 hours, followed by daily long-term (12h) infusion of 0.04 mg/kg/h over 5 days, “alteplase dosing regimen B”
- standard of care

in a 1:1:1 ratio, stratified according to ventilation (invasive mechanical vs. non-invasive).

In Part 2, patients will be randomised to

- alteplase (one dosing regimen), depending on results of Part 1. Accordingly, the following dosing regimen will be carried forward in Part 2: alteplase 0.6mg/kg over 2 hours, followed by daily long-term (12h) infusion of 0.04 mg/kg/h over 5 days, “alteplase dosing regimen B”
- standard of care

in a 2:1 ratio, stratified according to baseline ventilation status (invasive mechanical vs. non-invasive) and baseline D-Dimer level (\geq ULN to <5 vs \geq 5-fold ULN).

Throughout this whole Section, the NIV (non-invasive ventilation) patient cohort are those with a baseline WHO value of 6, and the IMV (invasive mechanical ventilation) patient cohort are those with a value 7, 8 or 9 at baseline.

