A sensitivity analysis of the primary endpoint (main estimand) will be carried out on the PPS, in line with the primary analysis.

Following the amendment to the inclusion criteria (CTP Version 4.0), whereby the original D-Dimer level changed from ≥ 3 -ULN to \geq ULN, some additional analyses will be performed. Firstly, a sensitivity analysis will be added, similar to the primary analysis, just replacing the baseline D-Dimer status on the two levels with that on the three levels (\geq ULN to < 3 , ≥ 3 to < 5 , ≥ 5 -ULN). Secondly, a supplementary analysis will be added, similar to the primary analysis, but removing all patients with baseline D-dimer status \geq ULN to < 3 -ULN, which is according to the expanded inclusion criteria.

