3. INTRODUCTION

As per ICH E9 ([1](#)), the purpose of this document is to provide a more technical and detailed elaboration of the principal features of the analysis, as described in the clinical trial protocol (CTP) Version 3 (c32434345-03, [2](#)). It will detail the procedures for executing the statistical analysis of the primary, all secondary endpoints, and other data, and will be limited to the analysis of Part 2 of BI trial 0135-0347.

CTP Version 3 is the updated CTP, following the interim results of Part 1. This TSAP assumes familiarity with CTP Version 3. In particular, the TSAP is based on the planned analysis specifications as written in CTP Version 3 Section 7 “Statistical Methods and Determination of Sample Size”. Therefore, TSAP readers may consult the CTP Version 3 for more background information on the study, e.g., on study objectives, study design and population, treatments, definition of measurements and variables, and planning of sample size and randomisation.

The NIV (non-invasive ventilation) patient cohort are those with a baseline WHO value of 6, and the IMV (invasive mechanical ventilation) patient cohort are those patients with a value of 7, 8 or 9 at baseline. All analyses will be performed within the NIV patient cohort as the main cohort for confirmatory purposes, and separately within the IMV patient cohort for exploratory purposes. This is consistent with the hierarchy testing approach following the primary and key secondary objectives of the statistical analysis, as outlined in CTP version 3 Section 7. Select analyses will be performed on the NIV and IMV cohorts pooled and the extent of the analyses will depend on the homogeneity observed of the two groups.

A database snapshot will be made when all patients have completed the day 28 visit and when the data has been cleaned. At this point, all analyses outlined in this Trial Statistical Analysis Plan (TSAP) will be performed, except for all cause mortality (ACM) at day 90. This further endpoint will be available at a later timepoint. When this data is available, then another snapshot will be taken, the database will be locked, and this endpoint will be analysed.

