11. HISTORY TABLE

Table 11: 1 History table

Version	Date	Author	Sections changed	Brief description of change
1	26-OCT-2021	[REDACTED]	None	This is the final TSAP

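### The Part 2 SAP's D-dimer covariate has no level for patients between ULN and 3-fold ULN, whom the current protocol admits and puts in the lower stratum

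*SAP*

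**What the plan says.** **Current protocol.** Inclusion criterion 5 (Section 3.3.2) requires D-dimer at or above the "upper limit of normal (ULN) according to local laboratory". Section 7 randomises Part 2 "in a 2:1 ratio, stratified according to baseline ventilation status (invasive mechanical vs. non-invasive) and baseline D-Dimer level", with D-dimer levels of ULN to below 5-fold versus 5-fold ULN or more; Section 7.4 repeats these strata. Section 7.2.2 records the change ("Following the amendment to the inclusion criteria (CTP Version 4.0), whereby the original D-Dimer level changed from" 3-fold ULN to ULN) and adds two analyses of the primary endpoint:

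- a sensitivity analysis, "just replacing the baseline D-Dimer status on the two levels with that on the three levels" (ULN to <3, 3 to <5, 5-fold or more);
- a supplementary analysis, "similar to the primary analysis, but removing all patients with baseline D-dimer status" from ULN to below 3-fold.

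**Part 2 SAP.** Section 3 states that "the TSAP is based on the planned analysis specifications as written in CTP Version 3 Section 7". The history table (Section 11) lists one version, dated 26-OCT-2021, with the remark "This is the final TSAP". Section 7 sets the default covariates for both the NIV and the IMV cohort, including "Baseline D-Dimer status (≥ 3 to < 5"-fold and 5-fold ULN or more. The same two levels appear in the IRT/CRF rule (Sections 7 and 7.1), the Kaplan-Meier strata (7.4.1) and the pooled-cohort models (7.4.2, 7.5.1.2, 7.5.2). The pooled model for major bleeding leaves D-dimer out.

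**The concern.** The default covariates feed the Cox model for H0_1 (SAP 7.4.1), the logistic models with average marginal effects for H0_2 and H0_3 (7.5.1.1) and the ANCOVAs (7.5.2). A patient whose D-dimer is twice ULN is eligible, randomised and in the full analysis set, but has no value for a covariate in any of these models. Section 7.1 makes the CRF value override the IRT stratum, so the IRT record does not settle the level. Section 6.6 deals with missing endpoint data and AE dates, not with a covariate value outside every listed level.

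Taken literally, the SAP leaves three ways to proceed, and each corresponds to a different analysis in protocol Section 7.2.2: primary, sensitivity or supplementary. In an open-label trial, the covariate behind three confirmatory tests should be written down in the SAP before the data snapshot rather than worked out by the programmer.

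**Working it through.** **1. Coverage of the levels (multiples of ULN).**

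| Source | Range covered |
|---|---|
| Eligible (protocol 3.3.2) | 1 and above |
| Protocol strata (7, 7.4) | 1 to <5; 5 and above |
| Part 2 SAP levels (7) | 3 to <5; 5 and above |

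The interval from 1 to <3 is eligible and lies in the protocol's lower stratum, but it has no SAP level.

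**2. The three readings.**

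| Handling of patients at 1 to <3 | Matching protocol analysis (7.2.2) |
|---|---|
| Merge into the lower level | Primary |
| Code as a third level | Sensitivity |
| Drop from the model | Supplementary |

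Dropping would also contradict the SAP's own rule that the primary and key secondary endpoints are analysed on the FAS (5.1, 5.2.1), because the FAS definition (6.3) has no D-dimer condition.

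**3. Omitted analyses.** SAP Section 7.4.2 lists the two bail-out estimands, the unadjusted model, the subgroups, the centre grouping and the pooled cohort model. Neither of the two D-dimer analyses is there.

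**4. Size, if patients were dropped.** Inputs from protocol Section 7.5: 70 SOC and 140 alteplase NIV patients; two-sided alpha 5%; HR 2.0 with event rates 30% and 50%; treatment failure 40% versus 20%; mortality 25% versus 9%.

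The plan's own power comes first:

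- H0_1: events = 70×0.30 + 140×0.50 = 91. Power = Φ(ln 2 × √(91×2/9) − 1.96) = Φ(3.117 − 1.96) = 87.6%.
- H0_2 and H0_3: power = Φ((d − 1.96·se0)/se1), with se0 from the pooled rate and se1 from the separate rates.
  - H0_2: Φ((0.20 − 1.96×0.0647)/0.0676) = 86.0%.
  - H0_3: Φ((0.16 − 1.96×0.0513)/0.0571) = 85.1%.

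These agree with the stated 85% to 90% for the first two steps and 85% for the third.

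Now remove a share x of NIV patients equally from both arms, with effects unchanged. No document gives x, so the values are assumptions.

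| x | NIV patients left | Events | H0_1 | H0_2 | H0_3 |
|---|---|---|---|---|---|
| 0 | 210 | 91.0 | 87.6% | 86.0% | 85.1% |
| 10% | 189 | 81.9 | 84.1% | 82.4% | 81.5% |
| 20% | 168 | 72.8 | 79.6% | 77.9% | 77.2% |
| 30% | 147 | 63.7 | 74.1% | 72.5% | 72.0% |

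As a check on the formula, stricter inputs are the HR implied by 30% and 50% under proportional hazards, ln 0.5/ln 0.7 = 1.943, and unpooled variance, Φ(d/se1 − 1.96). These give 84.8/84.1/80.0% at x = 0 and 80.9/80.1/75.7% at 10%. The absolute levels shift, but the loss at 10% is similar: 3.6 to 3.7 points in the base set and 3.9 to 4.3 in the stricter one.

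**The case against.** The strongest reply is that this is version lag between two files, not a choice anyone made for the current population. The SAP matched CTP Version 3, a later SAP may exist outside the supplied file, and this sponsor does revise its SAPs (the Part 1 SAP reached Version 2.0). The protocol's statement that the two analyses will be added also looks forward.

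The current protocol moreover already fixes the answer. Section 7.2.2 describes the primary coding as two-level, and Sections 7 and 7.4 place these patients in the lower level. SAP Section 7.1 itself treats baseline D-dimer as a randomisation stratification factor, so the identity of the variable is clear even though its printed levels are out of date. On that view only the merged reading is live, and the power figures describe an analysis nobody should run, at shares that no document supports.

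Most of this stands, and it limits the severity. It does not remove the mismatch. The supplied SAP still states levels that do not fit the trial population, and it still lacks two analyses the protocol requires. That second gap remains however the covariate is read.

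**Conclusion.** The concern holds as a point that should be fixed. The supplied Part 2 SAP is not aligned with the lowered D-dimer criterion, and the misaligned covariate sits in all three confirmatory tests.

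The numerical effect is zero if patients at ULN to below 3-fold are merged into the lower level, which is the coding the protocol implies. Power is lost only if they are dropped: about 3.6 to 4.3 points at an assumed 10% share, and more at larger shares. Those figures assume equal shares in both arms and unchanged effects.

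Two limits apply. Whether a later SAP exists cannot be told from the documents. SAP Sections 5.4 (baseline definitions) and 6.4 (subgroups) are not in the supplied text and could not be checked, although both belong to the same pre-amendment version.

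**What to change.** Before the Day 28 snapshot, update the Part 2 SAP to the current protocol:

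- In Sections 7, 7.1, 7.4.1, 7.4.2, 7.5.1.2 and 7.5.2, replace the lower D-dimer level with ULN to below 5-fold ULN. Check Sections 5.4 and 6.4 for the same coding.
- In Section 7.4.2, add for the primary endpoint the three-level sensitivity analysis and the supplementary analysis without patients at ULN to below 3-fold ULN, as in protocol Section 7.2.2.
- Update the protocol version cited in Section 3 and add an entry to the history table.

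The cost is SAP wording only. D-dimer is already collected for eligibility, and sample size and trial conduct are unaffected.

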7.1 DEMOGRAPHIC AND OTHER BASELINE CHARACTERISTICS

Only descriptive statistics are planned for this section of the report. See [Section 5.4](#) for specific definitions.

For the two randomisation stratification factors at baseline, baseline ventilation support (NIV, IMV) and baseline D-Dimer level (≥ 3 to < 5 , ≥ 5 -fold ULN), any discrepancies between the IRT and the CRF will be documented and summarized. Should there be a discrepancy between the value used for the randomisation stratification and the actual value as determined on the CRF, the actual value as determined on the CRF will be used in the analyses.

Within this section, all analyses will be performed on the NIV patient cohort, the IMV patient cohort and on the NIV and IMV cohorts pooled.

7.2 CONCOMITANT DISEASES AND MEDICATION

Medical history, COVID-19 signs and symptoms and concomitant diagnoses will be presented and coded using MeDRA System Organ Class and Preferred Term where possible.

Regarding concomitant medications, there is a specific question asking if the treatment was given as part of standard of care for the treatment of COVID-19, which is relevant for all patients since they all receive SOC in the background. This question is different to the randomised treatment assignment. Therefore, all concomitant medication analyses or displays will be split by 'Standard of Care for the treatment of COVID-19', yes or no. All concomitant medications will be coded using the WHO Drug dictionary.

Medications of special interest for COVID (as indicated by WHO, see [Section 10.1](#)), and restricted medications within this study (as outlined in CTP Version 3 Section 4.2.2.1, see [Section 10.2](#)) will also be summarized and split by whether or not the medication was given as part of the Standard of Care for the treatment of COVID-19.

Use of heparin will be summarized and presented.

Therefore, only descriptive statistics are planned for this section of the report.

Within this section, all analyses will be performed on the NIV patient cohort, the IMV patient cohort and on the NIV and IMV cohorts pooled.

7.3 TREATMENT COMPLIANCE

Only descriptive statistics are planned for this section of the report, and due to the nature of the study, compliance will be determined for the alteplase treatment group only.

Compliance to intake of infusion will be assessed in terms of % taken, as measured by volume, at each planned infusion. Overall compliance will be as an average measure of the %taken. The detailed definitions are provided in [Section 5.4](#).

Compliance with preparation of the infusion in terms of concentration, as indicated in CTP Version 3 Table 10.4 are also assessed, and detailed definitions provided in [Section 5.4](#).

Within this section, all analyses will be performed on the NIV patient cohort, the IMV patient cohort and on the NIV and IMV cohorts pooled.

7.4 PRIMARY ENDPOINT

Within this section, all descriptive analyses will be performed on the NIV patient cohort, the IMV patient cohort and on the NIV and IMV cohorts pooled.

7.4.1 Primary analysis of the primary endpoint

For the primary endpoint, a Cox proportional hazards model will be used to estimate the hazard ratio (HR) comparing alteplase to SOC. From the model, the 95% confidence intervals (CI) and corresponding Wald p-values for the HRs will be produced. The model will include fixed effects for treatment (alteplase, SOC), and the default set of covariates for the respective NIV or IMV patient cohorts, as outlined in [Section 7](#).

Kaplan Meier estimates will be presented by treatment (alteplase, SOC) for this endpoint up to day 28, and additionally, for the NIV patient cohort:

- treatment and baseline D-Dimer status (≥ 3 to < 5 , ≥ 5 -fold ULN)
- treatment and age (\leq median, $>$ median)
- treatment and number of days of NIV support (\leq median, $>$ median)

and for the IMV patient cohort:

- treatment and baseline D-Dimer status (≥ 3 to < 5 , ≥ 5 -fold ULN)
- treatment and age (\leq median, $>$ median)
- treatment and baseline WHO status (7, 8, 9)

From the KM estimates at various timepoints (days 6, 8, 12, 16, 20, 24 and 28) the risk difference (RD) for the treatments with 95% CI will be estimated by taking the difference of the individual probabilities. Since the observations in the two treatment groups are

independent, the variance of the Kaplan-Meier probability difference is equal to the sum of the Kaplan Meier probabilities' variances found by Greenwood's method. The 95% CI of the RD is therefore calculated accordingly.

7.4.2 Sensitivity analysis, subgroup analysis, exploratory analysis of the primary endpoint

Two non-confirmatory supplementary analyses will be conducted, in anticipation of the rare situation where bail-out therapy may be used (as defined in CTP Version 3 Section 4.2.2). They will be performed on the FAS.

The first of these supplementary analyses will address the treatment policy estimand, whereby there is no consideration for the intake of bail-out therapy.

The second of these supplementary analyses will address a composite estimand, whereby patients receiving bail-out therapy will be censored at day 28, rather than on the day of bail-out. Here, bail-out represents treatment failure and thereby, by definition, precludes any response after bail-out. The various scenarios are summarized in [Table 7.4.2: 1](#) below.

In both cases, and in the unlikely event that a patient discontinues from the study, prior to being able to determine if he had clinical improvement or hospital discharge, or had intake of bail-out therapy or death, he will be censored at the time of withdrawal.

Table 7.4.2: 1 Censoring of the primary endpoint for the treatment policy and composite estimands

Scenarios	Treatment policy estimand	Composite estimand
Bail-out then death	Censor at day 28	Censor at day 28
Bail-out then failure to improve#	Censor at day 28	Censor at day 28
Bail-out then clinical improvement / hospital discharge	Positive event at clinical improvement / hospital discharge	Censor at day 28
Bail-out then clinical improvement / hospital discharge then death	Positive event at clinical improvement / hospital discharge	Censor at day 28
Clinical improvement / hospital discharge regardless of subsequent events	Positive event at clinical improvement / hospital discharge	Positive event at clinical improvement / hospital discharge
Death only, prior to day 28	Censor at day 28	Censor at day 28
Failure to improve# by day 28	Censor at day 28	Censor at day 28
Discontinued from study due to withdrawal of consent prior to clinical improvement / hospital discharge or Bail-out/Death	Censor at time of study discontinuation	Censor at time of withdrawal

Clinical improvement / hospital discharge refers to the first of clinical improvement or hospital discharge, whichever comes first.

#Failure to improve is failure to have clinical improvement or hospital discharge.

The analyses performed will be identical to that outlined for the primary endpoint in [Section 7.4.1](#).

Based on the main estimand, the treatment effect will be estimated using the Cox proportional hazard model, containing only treatment in the model. The HR (95%CI) and p-value estimating the unadjusted treatment effect will be produced.

The effect of the subgroups in the NIV patient cohort, as outlined in [Section 6.4](#), related to the primary endpoint, main estimand, will be assessed descriptively and using Kaplan Meier estimates. Using the Cox proportional hazard model, hazard ratio estimates with 95% CI will be estimated from the model in two different methods:

- Firstly, in a model containing treatment, subgroup and the treatment * subgroup interaction.
- Secondly, in the model containing the default set of covariates as outlined in [Section 7.4.1](#) with this additional covariate added.

A covariate adjusted sensitivity analysis of the primary endpoint, main estimand, will be conducted, to determine the effect of the grouping of centres according to similar types of Standard of care. This will be the same analysis.

For the NIV and IMV cohorts pooled, the Cox proportional hazard model will be used, including the fixed effects for treatment (alteplase, SOC), baseline D-Dimer status (≥ 3 to < 5 , ≥ 5 -fold ULN), age and baseline ventilation status (NIV, IMV). From this model, the HR and 95% CI will be produced. In addition to this model, the interaction term for the baseline ventilation status and treatment will be included, and the p-value for this additional term will be used as a test of homogeneity. If the p-value is > 0.05 the it can be considered that the two groups are homogeneous, with respect to this primary endpoint.

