4. CHANGES IN THE PLANNED ANALYSIS OF THE STUDY

The screened set (SCR) and pharmacokinetic set (PKS), not outlined in CTP Version 3, are now defined in [Section 6.3](#). They are needed to summarise those patients to be included in the disposition flow and the PK analysis.

Subgroup analyses not included in CTP Version 3 are now outlined in Sections [6.4](#), [7.4.2](#) and [7.5.2](#) for the primary endpoint and one of the secondary endpoints. These analyses are to be used to test the robustness of the main analyses for that particular endpoint and to investigate if any of the subgroups are having an overwhelming influence on the study results.

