7.5.2 Other Secondary endpoints

Other secondary endpoints are defined in [Section 5.2.2](#). In all cases, standard descriptive statistics will be presented, whether the endpoint is binary or continuous.

Binary safety endpoint

For the binary safety endpoint MBE up to day 6, analysed on the TS, there will be no adjustment for covariates. Therefore, the RD will be the difference between the two incidences and the p-value and 95% CI will be determined using the Chan and Zhang exact method.

For the NIV and IMV cohorts pooled, the RD 95% CI will be estimated between the two treatment arms using the same approach as for the key secondary efficacy endpoints. However, for this pooled investigation of MBE up to day 6, the baseline D-Dimer status (≥ 3 to <5 , ≥ 5 -fold ULN) and age covariates will not be included in the model. The p-value for homogeneity will be determined similarly.

Continuous efficacy endpoints

The three other secondary endpoints which are continuous in nature will be analysed using a restricted maximum likelihood (REML) based ANCOVA comparing the outcome, by treatment. The ANCOVA model will be adjusted for the default set of covariates as outlined in [Section 7](#) for the respective NIV and IMV patient cohorts. The treatment difference with 95% CI and p-values will be presented.

For the continuous efficacy endpoints, number of OFDs at day 28, and number of days in hospital, there are not expected to be any missing values by definition and as outlined in [Section 5.2.2](#).

[figure not shown]
For the continuous efficacy endpoint change from baseline in the $\text{PaO}_2/\text{FiO}_2$ at day 6, the baseline $\text{PaO}_2/\text{FiO}_2$ will also be included in the model as covariate for adjustment. For patients that have died, or who have been discharged from hospital, the handling rules are as outlined in [Section 5.2.2](#). Note, there are expected to be very few deaths or hospital discharges prior to day 6.

In addition, subgroup analyses of this $\text{PaO}_2/\text{FiO}_2$ endpoint will be conducted in the NIV patient cohort only and using the subgroups as outlined in [Section 6.4](#). An ANCOVA model will contain the baseline $\text{PaO}_2/\text{FiO}_2$, the subgroup of interest and the interaction between subgroup and treatment.

As sensitivity analyses, the unadjusted treatment effects will be estimated, using the same approach as the main analysis, but with only treatment in the model.

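### No planned model gives covariate-adjusted treatment hazard ratios by subgroup in the NIV cohort, because the interaction model drops the default covariates and the adjusted model has no interaction

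*SAP*

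**What the plan says.** All references are to the Part 2 SAP unless stated otherwise.

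- **Purpose.** Section 4 gives the subgroup analyses two aims. One is to check that the main analysis is robust. The other is "to investigate if any of the subgroups are having an overwhelming influence on the study results".
- **Output.** Under 7.4.2, "hazard ratio estimates with 95% CI will be estimated from the model in two different methods".
- **Model 1.** "Firstly, in a model containing treatment, subgroup and the treatment * subgroup interaction". No other term is listed.
- **Model 2.** "Secondly, in the model containing the default set of covariates as outlined in" Section 7.4.1, "with this additional covariate added".
- **The base of model 2.** Section 7.4.1 has main effects only: "The model will include fixed effects for treatment (alteplase, SOC), and the default set of covariates for the respective NIV or IMV patient cohorts". Section 7 lists the NIV defaults as baseline D-dimer status, age and number of days of NIV support.
- **PaO2/FiO2 at Day 6.** The subgroup ANCOVA in 7.5.2 contains baseline PaO2/FiO2, "the subgroup of interest and the interaction between subgroup and treatment". The main ANCOVA for the same endpoint also carries the default covariates.
- **Pooled NIV and IMV cohorts.** Sections 7.4.2, 7.5.1.2 and 7.5.2 start from a covariate-adjusted model, add a treatment-by-ventilation interaction and use its p-value as a test of homogeneity.

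**The concern.** A reader of the subgroup results will set them beside the primary hazard ratio, which is adjusted for D-dimer status, age and NIV days. Neither subgroup model supplies a like-for-like comparison. Model 1 gives a hazard ratio per subgroup level, but unadjusted. Hazard ratios are non-collapsible: leaving out prognostic covariates pulls them towards 1 even when the arms are perfectly balanced. A forest plot of model 1 estimates beside the adjusted primary estimate would therefore mix two scales. Model 2 is on the right scale but has only one treatment coefficient, so it cannot show whether one subgroup drives the result. The second aim in Section 4 rests entirely on the unadjusted model, and no interaction p-value is requested for the NIV subgroups.

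**Working it through.** **1. Terms in each NIV model for the primary endpoint**

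| Model | Default covariates | Subgroup main effect | Treatment-by-subgroup | Treatment HR returned |
|---|---|---|---|---|
| 7.4.1 primary | yes | no | no | one, adjusted |
| 7.4.2 model 1 | no | yes | yes | one per level, unadjusted |
| 7.4.2 model 2 | yes | yes | no | one, adjusted |
| Not specified | yes | yes | yes | one per level, adjusted |

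The added covariate in model 2 is singular and follows a bullet that names the interaction separately. The plain reading is the subgroup main effect alone.

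**2. The plan's own figure**

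The point does not rest on a stated number, but the planning figure gives the scale. Protocol 7.5 assumes HR 2.0, event rates of 30% (SOC) and 50% (alteplase), 70 and 140 NIV patients, and two-sided alpha of 5%.

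- Expected events: 0.30 × 70 + 0.50 × 140 = 21 + 70 = 91.
- Schoenfeld: SE(log HR) = 1/√(91 × 1/3 × 2/3) = 0.222.
- Power = Φ(ln 2 / 0.222 − 1.96) = 87.6%, inside the stated 85% to 90%.

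**3. Precision of any interaction test here**

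With two equal halves, SE(log ratio of HRs) = 2 × 0.2224 = 0.445.

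- Power for a ratio of hazard ratios of 2: Φ(0.693/0.445 − 1.96) = 34%.
- Ratio detectable with 80% power: exp((1.96 + 0.842) × 0.445) = 3.48.

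Interaction tests in this cohort are weak whichever model is used.

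**4. Cost of omitting the covariates (assumed inputs)**

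The documents give no covariate effects, so the following are assumptions:

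- 210 patients, 2:1, two subgroups of equal expected size, with true conditional HRs of 3.0 and 1.33;
- three standard normal covariates with log-HRs of −0.5, −0.4 and −0.4, and a subgroup main effect of 0.3 on the log scale;
- baseline hazard 0.0115 per day, censoring at Day 28, 400 runs.

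The simulated event rates run a little above the planned 30% and 50%.

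| Model | HR, subgroup with true 3.0 | HR, subgroup with true 1.33 | Log interaction (true −0.81) | Interaction power |
|---|---|---|---|---|
| 1 as written | 2.63 | 1.30 | −0.70 | about 30% |
| 2 as written | 2.08 | 2.08 | none | none |
| Covariates and interaction | 3.12 | 1.35 | −0.83 | about 38% |

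The Monte Carlo SE of each power is about 2 points, e.g. √(0.295 × 0.705/400) = 0.023. HRs are exponentiated mean log-HRs.

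**5. Range**

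A second setting used true HRs of 3.0 and 1.0, 30% SOC events, and three covariates each with a log-HR of 0 to 0.7 per SD (300 runs per value). Over that range, model 1 estimates the larger HR at 3.04 falling to 2.21, and its interaction power falls from 57% to 39%. With covariates and interaction together, the HRs stay near 3.0 and 1.0 and power stays at 56% to 61%. These figures move somewhat with the random seed, but the direction does not. If the covariates are not prognostic, nothing is lost.

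**The case against.** The strongest case for the plan is that the two models match the two aims in Section 4. Model 2 asks whether the adjusted hazard ratio is stable when the subgroup factor is added. Model 1 asks whether the effect differs by subgroup. An unadjusted interaction model is valid in a randomised trial. Section 7.4.2 also plans an unadjusted overall hazard ratio, which is a natural comparator for model 1, and 7.4.1 plans Kaplan-Meier curves by treatment within D-dimer, age and NIV-day categories. For PaO2/FiO2, 7.5.2 keeps the baseline value in the subgroup model.

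Most of this stands, and it rules out several stronger readings:

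- *The plan cannot detect a subgroup difference.* Not so: model 1 can, and on the inputs above it shows one (2.63 against 1.30).
- *Neither model gives any adjusted subgroup effect.* Model 2 does give an adjusted prognostic (main) effect of the subgroup, and a treatment effect adjusted for it. Only the adjusted treatment effect by subgroup is missing.
- *Model 2 is redundant.* It would repeat the primary model if D-dimer status were a subgroup. The list of subgroups in Section 6.4 is not in the public text, so this cannot be asserted.
- *Model 1 is biased by chance imbalance.* Nothing here quantifies that. What the simulation shows is mainly attenuation from omitted prognostic covariates.

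What survives is narrow. The unadjusted overall estimate helps interpret model 1, but no subgroup estimate is on the scale of the primary result, although the same SAP puts an interaction into adjusted models for ventilation status.

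**Conclusion.** The point holds as a gap in specification: no planned model gives covariate-adjusted alteplase hazard ratios by subgroup in the NIV cohort, and the PaO2/FiO2 subgroup ANCOVA omits the default covariates used in its main analysis. The consequence is modest. On assumed inputs, model 1 pulls the larger hazard ratio from 3.0 to 2.63, and interaction power is about 30% instead of 38%. The loss is nil if the covariates do not predict outcome and grows as they do. The corrected model remains underpowered for interaction, so it improves comparability more than detection. A reader might infer that the trial's conclusion is at risk, but it is not: these analyses are exploratory and lie outside the hierarchical test of H0_1 to H0_3 in protocol 7.1. The reading assumes that the added covariate in model 2 is the subgroup main effect and that the unseen Section 6.4 specifies no further model. This is a free improvement.

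**What to change.** Keep both existing models and the unadjusted overall estimate.

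1. In 7.4.2, extend the adjusted model to treatment + default covariates + subgroup + treatment-by-subgroup. When the subgroup factor is itself a default covariate, enter it once.
2. Report the hazard ratio and 95% CI at each subgroup level and the interaction p-value, labelled exploratory. The pooled cohorts already have an interaction p-value for ventilation status.
3. In 7.5.2, add the default covariates to the PaO2/FiO2 subgroup ANCOVA, with the same rule against double entry.

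The cost is SAP wording and one more model per subgroup factor. The covariates are already collected and already used in the primary analysis; no sample size, alpha or data collection changes. The Part 2 SAP is written to protocol Version 3 and still uses D-dimer categories starting at 3-fold ULN, whereas the current protocol starts at ULN. It therefore needs revising anyway, and this change can be made in the same update, before the Day 28 snapshot.
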